#### Skin Redness or Rash – Severity Category

1. On a scale of 1 to 10, where 1 is very little, and 10 is severe, how would you rate the redness of your skin or rash?
  - If 1-5, do not record as AE, **unless itchiness and/or pain are moderate**
  - If 6-7, Mild AE
  - If 8-9, Moderate AE**
  - If 10, Severe AE**
2. Are you experiencing **pain or itchiness** where your skin is red or where you have a rash?
  - If no, stop.
  - If yes, on a scale of 1 to 10 where 1 is very little, and 10 is severe, how would you rate the **itchiness**?
    - If 1-5, do not record as AE
    - If 6-7, Mild AE
    - If 8-9, Moderate AE**
    - If 10, Severe AE**

- If yes, on a scale of 1 to 10 where 1 is very little, and 10 is severe, how would you rate the **pain**?
  - If 1-2, do not record as AE
  - If 3-5, Mild AE
  - If 6-8, Moderate AE**
  - If 9-10, Severe AE**

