## 23. Appendix B

### Adverse Events Severity and Relatedness Questions

May 2017

When patients share a complaint, program coaches will identify the complaint in the Anticipated Complaints Guidebook. Based on the complaint type, coaches will then ask questions to determine:

1. Severity of the complaint (e.g., Mild, Moderate, or Severe), and
2. Relatedness of the complaint to the use of program devices (e.g., Not Related, Probably Not Related, Possibly Related, and Probably Related)

Coaches will document answers in the templates provided, including the Adverse Event document.

If the complaint falls in any of the severity categories highlighted in red, the coach will make a “warm transfer” to the study doctor and/or his staff so that the patient can be scheduled for an ancillary appointment.

If the complaint is an emergency, patients will be instructed to call 911.

If a patient has a complaint that is not listed in the Anticipated Complaints Guidebook, the coach can “warm transfer” the patient to the study clinic for guidance. The coach will document as much as possible in Adverse Event document. Follow up with the clinic will determine severity and relatedness.

Coaches will contact the PI when situations arise that are not covered in the Anticipated Complaints Guidebook.

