### **Insertion Site Bruising – Severity Category**

1. On a scale of 1 to 10, where 1 is very little, and 10 is severe, how much bruising do you have?
  - If 1-5, do not record as AE, **unless the bruise is getting bigger, see question 2**
  - If 6-7, Mild AE
  - If 8-9, Moderate AE
  - If 10, Severe AE
2. Is the bruise or bump getting bigger?
  - If no, stop
  - If yes, **Moderate AE**
  - If yes and bruise is significantly getting bigger, **Severe AE**

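### Redness/rash script: with redness of 1-5, mild itch or pain is left unrecorded by question 1 but graded a Mild AE by question 2, and no rule decides between them

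*Combined protocol and SAP*

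**What the plan says.** The opening of Appendix B has coaches determine two things about a complaint: "Severity of the complaint (e.g., Mild, Moderate, or Severe), and" its relatedness to the program devices. The wording treats severity as one grade per complaint.

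In the skin redness or rash severity script, question 1 asks for a redness score from 1 to 10. For the lowest band the instruction is "If 1-5, do not record as AE", with one exception: "unless itchiness and/or pain are moderate". Mild is not named in that exception.

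Question 2 asks about pain or itchiness "where your skin is red or where you have a rash" and scores each from 1 to 10:

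- Itch of 1-5 is not recorded and 6-7 is a Mild AE. The next band is "If 8-9, Moderate AE", and 10 is Severe.
- For pain, the lowest band is "If 1-2, do not record as AE" and 3-5 is a Mild AE. Then comes "If 6-8, Moderate AE", and 9-10 is Severe.

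The bruising script is built the same way. Its low scores are also left out "unless the bruise is getting bigger, see question 2". There, an enlarging bruise is Moderate or Severe under question 2, so the exception and the later question agree.

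**The concern.** Take a participant with redness 3, itch 2 and pain 4. Under question 1 the redness is in the unrecorded band and neither symptom is moderate, so nothing is entered. Under question 2 the pain alone makes a Mild AE. Two coaches hearing identical answers can each follow a line of the script and produce different records.

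The sensor is investigational. Section 9 lists redness, itch and pain among its expected events and provides for AE reporting to the IRB, the manufacturer and the FDA under regulations and standard procedures. Planned exposure is large: 500 participants for 10 weeks (70 days) on 10-day sensors is 500 × 70/10 = 3,500 sensor periods if everyone completes. If coaches resolve the script differently, the count of mild skin events reflects the coach as well as the device. A tally made afterwards cannot correct this unless the underlying scores were kept.

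**Working it through.** The plan gives no figure to reproduce. The check enumerates all itch-by-pain score pairs for a participant with redness of 1-5, using only the cut-points in the redness or rash script.

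| Question 2 grade | Itch scores | Pain scores |
|---|---|---|
| Not recorded | 1-5 (5 values) | 1-2 (2 values) |
| Mild | 6-7 (2 values) | 3-5 (3 values) |
| Moderate | 8-9 (2 values) | 6-8 (3 values) |
| Severe | 10 (1 value) | 9-10 (2 values) |

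Total pairs: 10 × 10 = 100 for each redness score from 1 to 5. The script does not say how the itch and pain grades combine, so I take the worse of the two (an assumption).

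**Step 1: question 1's exception not met.** Read moderate as moderate or worse. The exception fails when itch is 1-7 and pain is 1-5: 7 × 5 = 35 pairs.

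**Step 2: both questions leave the complaint out.** Itch 1-5 and pain 1-2: 5 × 2 = 10 pairs.

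**Step 3: conflict.** 35 − 10 = 25 pairs are unrecorded under question 1 and Mild under question 2. They are made up of:

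- itch unrecorded, pain mild: 5 × 3 = 15
- itch mild, pain unrecorded: 2 × 2 = 4
- both mild: 2 × 3 = 6

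The sum is 15 + 4 + 6 = 25.

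**Step 4: sensitivity to the reading of moderate.** If moderate means exactly moderate, the exception fails for itch 1-7 or 10 combined with pain 1-5 or 9-10: 8 × 7 = 56 pairs. The same 25 conflicts with Mild remain, and 56 − 35 = 21 further pairs become unrecorded under question 1 but Severe under question 2. The moderate-or-worse reading is thus the more favourable one to the plan.

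**Step 5: one symptom absent.** Allowing a zero for itch or pain, but not both, gives 11 × 11 − 1 = 120 pairs. Conflicts are 6 × 3 + 2 × 3 + 2 × 3 = 30, and 30/120 = 25%.

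The count of 25 in 100 therefore does not depend on how moderate is read, and the proportion is unchanged when a symptom may be absent.

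**The case against.** The best defence is that the two questions govern different things. Question 1 would decide whether low-grade redness is itself an AE, while question 2 records itch and pain in their own right. The stand-alone itch script uses the same itch bands, and the insertion-site pain script uses the same numeric bands, although it rates effect on daily activities. Redness 3 with pain 4 would then mean that the redness is not recorded and the pain is a Mild AE. This is coherent, and it is why I call the script unreconciled rather than flatly impossible to follow. But the script does not say it. It also fits poorly with question 1's exception: if itch and pain were always recorded independently, redness would have no need to refer to them. A coach cannot tell from the page which reading is meant.

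Three further points stand and limit the finding:

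- In 15 + 4 = 19 of the 25 pairs, question 2 is itself split, with one symptom unrecorded and the other Mild. The count relies on the worst-grade assumption.
- The consequence is modest. Section 10 names no AE endpoint or comparison, and the study disclaims hypothesis testing. Sections 6 and 9 have the study doctor's coordinator assess events, so the coach's script is not the only assessment.
- Appendix B already has coaches write answers into templates. The templates are not in the document, so a reader might infer that raw scores are lost, but that cannot be shown.

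**Conclusion.** The point holds as an unresolved recording rule inside one script. At redness 1-5, 25 of 100 itch-by-pain score pairs receive different instructions from questions 1 and 2, given the worst-grade assumption. With moderate read as moderate or worse, recording of moderate and severe itch or pain is consistent across the two questions and only mild events are affected. It is worth correcting because the rule feeds device AE counts, but it does not touch the study's primary aim.

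The documents do not support some stronger readings that a reader might infer:

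- *A quarter of patients or events are affected.* The 25 in 100 weights all score pairs equally, and no distribution of scores is given.
- *Most of what question 1 leaves out is in conflict.* That share is 25/35 = 71% if moderate means moderate or worse, but 25/56 = 45% if it means exactly moderate. Only the 25 is stable.
- *Aligning the script with Section 9 could not help.* It could. Section 9 describes itch as severe and pain as 8 or more out of 10. Carrying those definitions into question 2 would remove the Mild bands and with them the conflict. I do not judge which threshold is right.
- *Counts will differ by coach.* They could; nothing in the documents shows how coaches apply the script.

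**What to change.** Reconcile questions 1 and 2 into one recording rule. It should state whether itch and pain at a red or rash site are recorded as separate AEs or combined with redness into one grade, and in the latter case how. It should also say whether moderate in the exception means moderate or worse. The choice of threshold is for the sponsor and the study doctor.

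Separately, confirm that the coaches' templates keep the raw redness, itch and pain scores for every complaint, including those not recorded as AEs. The chosen rule can then be applied identically to all participants, including any assessed before the edit.

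The cost is about one line of script, plus up to three numeric fields if the templates lack them. The mild AE count may change.

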#### **Skin Redness or Rash – Relatedness Category**

1. Where is the location of the redness or rash?
  - If in the same location as the sensor on your skin, then Probably Related
  - If in a location where a sensor was within 2 days, then Possibly Related
  - If in a location where a sensor was 2+ days in the past, then Probably Not Related
  - If in a location where a sensor was never placed, then Not Related

#### **Skin Itchiness – Severity Category**

1. On a scale of 1 to 10, where 1 is very little, and 10 is severe, how would you rate your skin itchiness?
  - If 1-5, do not record as AE
  - If 6-7, Mild AE
  - If 8-9, Moderate AE
  - If 10, Severe AE**

#### **Skin Itchiness – Relatedness Category**

1. Where is the location of the itchiness?
  - If in the same location as the sensor on your skin, then Probably Related
  - If in a location where a sensor was within 2 days, then Possibly Related
  - If in a location where a sensor was 2+ days in the past, then Probably Not Related
  - If in a location where a sensor was never placed, then Not Related

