- None of the expected device-related adverse events as defined in the protocol and associated documents would be life-threatening or would result in any permanent impairment of a body function or permanent damage to a body structure;
- There are no expected electrical safety risks as the device has passed the electrical safety tests as per EN45502-1 and EN60601;
- If the subject feels any discomfort during the course of the study, he/she will be able to remove the device immediately (the device is not permanent);
- The device is being used to complement, not replace, self-monitoring of blood glucose meter information, and readings are not intended to be used alone to make diabetes self-management decisions. As with the currently approved device and per intended use of similar technologies, subjects in the study will be instructed not to use the device for diabetes therapy or management;

- Subjects will be instructed to monitor their blood glucose levels as per their usual practice.

Adverse events (AE) associated with the use of the device include pruritus (severe itchiness present 48 hours after removal), erythema (reddening of the skin present 48 hours after removal), and inflammation (swelling and pain, defined as 8 or greater on a 10 point scale 48 hours after removal) where the adhesive touches the skin; local infection at insertion site; and shooting pain located at the site of the sensor (defined as 8 or greater on a 10 point scale). Rarely, the sensor wire will fracture when the sensor is being inserted, worn, or removed. If a sensor breaks and no portion of it is visible above the skin, the participant will be instructed to not remove it and seek medical care from the study doctor and/or his staff.

No serious adverse events (SAE) or Unanticipated Problems (UP) are expected as a result of participation in this minimal risk study. However, AE, SAE and UP will be monitored in the following ways:

- Participants in the study will be instructed to call the study doctor's clinical research coordinator to report all AE, SAE and UP related to the use of the CGM devices. The study doctor and/or his staff will assess the severity of any health problems associated with the device, and if needed, see the patient at the study clinic to assure appropriate care.

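### Appendix B codes a sensor-site reaction raised 2 or more days after removal as Probably Not Related, although Section 9 lists reactions still present at 48 hours as device-associated

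*Combined protocol and SAP*

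**What the plan says.** Section 9 (Assessment of Safety) names the AEs associated with use of the device. They include "pruritus (severe itchiness present 48 hours after removal), erythema (reddening of the skin present 48 hours after removal", and also "inflammation (swelling and pain, defined as 8 or greater on a 10 point scale 48 hours after removal", the latter located "where the adhesive touches the skin".

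Appendix B asks coaches to establish "Relatedness of the complaint to the use of program devices (e.g., Not Related, Probably Not Related, Possibly Related, and Probably Related". For itchiness the only relatedness question is "Where is the location of the itchiness". The site of the current sensor gives Probably Related, and a site where no sensor was ever placed gives Not Related. Between these are two time branches: "If in a location where a sensor was within 2 days, then Possibly Related" and "If in a location where a sensor was 2+ days in the past, then Probably Not Related". The forms for redness or rash, insertion site pain and insertion site swelling use the same branches.

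Three other places bear on the point:

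- Section 12 (Risks of CGM) tells participants who remove the device to expect reaction symptoms to clear within a week.
- Section 6 (Integration with patient care) has the coordinator assess severity and relatedness.
- Section 9 has coaches connect patients who report events with that coordinator, and describes Appendix B as guidance for coaches.

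**The concern.** Section 9 uses persistence to 48 hours as part of what makes the reaction a device-associated AE. Appendix B uses the same elapsed time as evidence against the device. The form does not ask when the symptom began, so a reaction that started under the sensor and never cleared gets the same code as a new complaint at an old site.

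The sensor is investigational, and one of the arguments in Section 9 for non-significant risk concerns the expected device-related AEs. Coaches write their answers into the Adverse Event document, and Section 9 places AE records from conversations with program staff in the Case Report Form. A code that contradicts Section 9 can therefore enter the study record. It would distort reported attribution only if it were carried forward in place of the coordinator's or study doctor's assessment.

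**Working it through.** The plan gives no figure to reproduce. The check sets the two sections against one clock: time since the sensor left the site.

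**Inputs.** The 48-hour mark is from Section 9. The 2-day branches are from the relatedness questions in Appendix B. The four relatedness categories are from the opening of Appendix B; I number them 1 (Not Related) to 4 (Probably Related) only to count steps. The one-week clearing time is from Section 12.

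**Common unit.** 48 hours / 24 = 2 days.

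| Sensor at the site | Section 9 mark reached? | Appendix B code (itchiness, redness) | Step |
|---|---|---|---|
| In place now | No | Probably Related | 4 |
| Removed less than 48 h ago | No | Possibly Related | 3 |
| Removed exactly 48 h ago | Yes | Possibly Related and Probably Not Related both fit | 3 or 2 |
| Removed more than 48 h ago | Yes | Probably Not Related | 2 |

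A reaction can be seen to meet the Section 9 timing only at 48 hours or later. Beyond that point, unless a new sensor sits on the same spot, the form allows only Probably Not Related.

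**Size per event.** Against coding during wear: 4 − 2 = 2 steps. Against coding within 2 days: 3 − 2 = 1 step.

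**Worked case.** A patient first tells the coach, 72 hours after removal, of itching scored 10. In Section 9 this is device-associated pruritus. In the Appendix B severity question it is "If 10, Severe AE". Since 72 / 24 = 3 days, which exceeds 2, the relatedness question makes it Probably Not Related.

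**Against the expected course.** If symptoms may take up to 7 days to clear, 7 − 2 = 5 of those 7 days fall in the late branch.

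**Illustration only.** Coach calls are scheduled weekly. Assume that removal falls uniformly between calls and that a reaction still present is raised only at the next call. The call then comes more than 2 days after removal in 5 / 7 = 71% of such cases. Patients can call sooner and many reactions will have cleared, so this is not an estimate of affected events. It shows only that the late branch is not a remote case.

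**Pain and swelling.** These forms use the same late branch but concern the insertion site, whereas the 48-hour inflammation in Section 9 is tied to the adhesive area. The conflict is less direct, although these are the only printed forms for swelling and for pain without redness.

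**The case against.** The strongest reply is that the coach's code is not the last word. The coordinator assesses relatedness, referral under Section 9 does not depend on the code, and warm transfer in Appendix B follows severity. This stands as a limit on the consequence. It does not remove the contradiction. Appendix B says that clinic follow-up will settle relatedness only for complaints outside its guidebook, and no readable text says which assessment prevails when two differ. The reporting chart in Appendix C might, but it cannot be read here.

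A second reply is that the 2 days could run from wear to the start of the reaction, so that a persistent reaction would escape the late branch. The form does not support this. It refers to the sensor now on the skin, is completed when the complaint is shared, and has no onset question. The unprinted Adverse Event document may record dates, but the printed rule does not use them.

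A third is that Section 9 lists types of event and does not rule on causality case by case, and that weaker attribution with time is a reasonable design. It is true that a late symptom may have another cause and that Probably Not Related leaves some room. But a rule based on location and elapsed time cannot separate a persisting reaction from a new one, and it sets its least favourable time branch at the very time that Section 9 uses to recognise the reaction.

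Finally, Section 10 plans no analysis of AE relatedness. That is correct, and the stake is the safety record, not an estimate or a test.

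**Conclusion.** The concern holds and should be fixed. For itchiness and redness or rash, Appendix B gives a relatedness code that contradicts Section 9 whenever a persisting reaction is first raised more than 2 days after removal. At exactly 2 days the form gives two answers. For pain and swelling the mismatch is real but weaker.

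The effect is one or two steps on a four-step scale per affected event. Frequency is unknown. Reactions coded during wear or within 2 days are unaffected, and neither AE recording nor the severity grade depends on the code. The conclusion rests on reading the 2 days as running from when the sensor left the site to the call. An effect on reported attribution further requires that the coach's code be carried forward unreviewed, which the readable documents neither state nor exclude.

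**What to change.** - Reconcile Section 9 with the relatedness questions for redness or rash, itchiness, pain and swelling, so that a reaction meeting a Section 9 definition is not coded Probably Not Related solely because it lasted past 2 days.
- Define the two time branches so that only one applies at 48 hours, and state that time is counted from sensor removal.
- Record the onset date and the sensor removal date for each site complaint, if the Adverse Event document does not already do so.
- Label the coach's code as preliminary and state that the coordinator's or study doctor's assessment is the one carried into reporting, in line with Sections 6 and 9.

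The cost is a short edit to the coach form and at most two date fields per site complaint. Somewhat more events may be attributed to the device.

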#### **Insertion Site Pain or Discomfort – Severity Category**

1. On a scale of 1 to 10, where 1 is very little, and 10 is severe, how much does your pain or discomfort affect your ability to do your daily activities?
  - If 1-2, do not record as AE
  - If 3-5, Mild AE
  - If 6-8, Moderate AE**
  - If 9-10, Severe AE**

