### **Detached/Broken Sensor Wire – Severity Category**

1. Do you see the sensor wire sticking out of your skin?
  - If no, then stop
  - If yes, then ask: On a scale of 1 to 10, where 1 is very little, and 10 is severe, how would you rate your pain or discomfort
    - If 1 – 7, **then Mild AE**
    - If 8 – 9, **then Moderate AE**
    - If 10, **then Severe AE**

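### The coach script for insertion-site pain scores only interference with daily activities, so it cannot identify the shooting-pain adverse event that Section 9 defines by a score of 8 or more

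*Combined protocol and SAP*

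**What the plan says.** Section 9 (Assessment of Safety) names the AEs associated with the device. One is "shooting pain located at the site of the sensor (defined as 8 or greater on a 10 point scale". Another is inflammation where the adhesive touches the skin: "swelling and pain, defined as 8 or greater on a 10 point scale 48 hours after removal". Neither definition refers to daily activities, and neither states what its 10 point scale measures.

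Appendix B (Section 23) holds the scripts with which "coaches will then ask questions to determine" severity and relatedness. The script headed Insertion Site Pain or Discomfort has a single severity item: "how much does your pain or discomfort affect your ability to do your daily activities". Its lowest band reads "If 1-2, do not record as AE". Scores of 3–5 are Mild, 6–8 Moderate and 9–10 Severe. No second question or override follows.

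Two other scripts in Appendix B rate pain directly. The Skin Redness or Rash script asks about pain "where your skin is red or where you have a rash", in the form "how would you rate the pain", and uses the same four bands. The Detached/Broken Sensor Wire script asks "how would you rate your pain or discomfort" once the patient reports a visible wire.

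**The concern.** The insertion-site script is the one a coach would open for a complaint of sensor-site pain alone. It collects a different quantity from the one that Section 9 appears to define, and it does not ask about the shooting character that Section 9 requires. A coach who follows it exactly ends the call without the two facts needed to decide whether the Section 9 event occurred. If the pain barely affects activities, the instruction is to record nothing.

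What is at stake is the completeness of one listed AE for an investigational device in the coach channel. Appendix B also links certain severity categories to a direct hand-over to the study doctor, so a complaint that receives no grade does not trigger that hand-over through the script.

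**Working it through.** The plan states no figure on this point, so there is none to reproduce. The check is a comparison of the texts, followed by a count of score combinations.

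**1. The rules side by side**

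| Place | Quantity scored | Not an AE | Mild / Moderate / Severe |
|---|---|---|---|
| Section 9, shooting pain | Unlabelled; read as intensity | below 8 | not graded |
| Appendix B, insertion-site pain | Effect on daily activities | 1–2 | 3–5 / 6–8 / 9–10 |
| Appendix B, pain item under redness or rash | The pain itself | 1–2 | 3–5 / 6–8 / 9–10 |
| Appendix B, broken wire (visible) | Pain or discomfort itself | none | 1–7 / 8–9 / 10 |

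The insertion-site script is the only one of the three Appendix B pain items that does not rate the pain. The redness and bruising scripts each have a further check when the first score is low (itch or pain; a growing bruise). The insertion-site script has none.

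**2. A worked case**

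Take shooting pain at the sensor site with intensity 9 and activity score 1.
- Section 9, read as intensity: an AE.
- Pain item under redness or rash, if the skin is also red: Severe.
- Insertion-site script: not recorded.

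**3. Crossing the two rules**

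Score both intensity and activity effect from 1 to 10, giving 10 × 10 = 100 combinations.
- Intensity 8–10: 3 × 10 = 30 combinations reach the Section 9 score. They meet the full definition only if the pain is also shooting.
- Of these, activity score 1–2: 3 × 2 = 6 are not recorded, so 6 of 30.
- Intensity 1–7: 7 × 10 = 70 combinations fall below the Section 9 score. With activity score 3–10, 7 × 8 = 56 of the 70 are recorded by the script.

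The mismatch therefore runs both ways. The cells are not equally likely, and the documents do not say how the two scores move together, so none of these counts is a rate.

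**4. What different remedies would do on the same grid**

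- Replace the activity score by intensity and keep the bands. Newly recorded: intensity 3–10 with activity 1–2, 8 × 2 = 16. Newly unrecorded: intensity 1–2 with activity 3–10, 2 × 8 = 16. The net change is zero, activity-limiting pain is dropped, and the shooting feature is still not asked.
- Keep the activity score and its bands, and add intensity and shooting as recorded items. The Section 9 event can then be identified in all 30 combinations when the pain is shooting, so unrecorded combinations fall from 6 of 30 to 0 of 30. Nothing now recorded is lost.

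**5. Exposure**

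Ten weeks is 70 days. With a 10-day sensor that is 70 / 10 = 7 sensors per participant, or 500 × 7 = 3,500 sensors under full wear by the intended enrolment. This is the opportunity for the event, not an estimate of how often it occurs.

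**The case against.** Grading pain by its effect on function is a legitimate choice, and nothing in the protocol requires all the scripts to rate the same quantity. The coach script is also not the only route. Section 6 (Integration with patient care) and Section 9 direct participants to the study doctor's research coordinator, who assesses severity and relatedness. Section 9 also has coaches connect patients who report an event to that coordinator. Pain is rated directly when it comes with redness, rash or a visible wire, and it forms part of the composite infection rating. The Anticipated Complaints Guidebook and the Adverse Event document are not reproduced, so what else they collect is unknown. All of this stands. It limits the likely loss, but it does not give this script the items needed to recognise the Section 9 event.

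A reader might infer more than the documents support:
- That Section 9 defines all sensor-site pain by a score. Its scored definitions cover shooting pain and, separately, inflammation.
- That the lost events are mostly brief, sharp pain on insertion. Section 9 mentions neither brevity nor insertion, and nothing in the documents shows that such pain seldom limits activities.
- That grades are usually wrong. With bands of width 2, 3, 3 and 2, the two quantities share a band in 4 + 9 + 9 + 4 = 26 of 100 combinations and differ in 74. That count weights every combination equally and says nothing about frequency.
- That a planned pooled pain count is compromised. Section 10 describes an exploratory evaluation without hypothesis tests and sets out no pooling of pain events across scripts.

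**Conclusion.** The point holds in a limited form, as a minor one. Followed as written, the stand-alone insertion-site script cannot identify the shooting-pain AE of Section 9, because it obtains neither the strength of the pain nor its character. Outright non-recording is confined to activity scores of 1 or 2. At 3 or more an AE is recorded, though its grade reflects interference and it cannot be matched to the Section 9 definition.

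The conclusion rests on reading Section 9's unlabelled scale as pain intensity, which is the natural reading but not an explicit statement. How many events would be missed cannot be computed. That would need the frequency of shooting pain scoring 8 or more, its joint distribution with activity scores, and the share that reaches the coordinator by another route. The documents give none of these, so a claim that the trial will materially undercount pain AEs would go beyond them.

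**What to change.** Keep the daily-activities question and its bands in the insertion-site script. Add two recorded items: a direct pain rating worded like the one in the redness and rash script, and a yes/no item on whether the pain is shooting. Identify and report the Section 9 pain AE from those two items whatever the activity score.

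Separately, the sponsor should reconcile Section 9 with the insertion-site script on which quantity and which cut-off make pain a recordable AE, and which quantity sets its severity grade. The script records from 3 on one quantity, whereas Section 9 starts at 8 on what appears to be another. Because the grades are tied to referral, no threshold or referral rule is proposed here.

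The cost is two short questions in the coach template and possibly a few more pain AEs recorded.
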